1.1.5. Safety analysis

- Safety endpoints and adverse effects during 3, 6 and 12 months post-procedure compared between the 2 groups (RDN-Treatment group vs. Sham group).
- Listing of AE and ADE in original term provided for each patient (Solo-Population)
Listing of SAE, AESI, SADE in original term provided for each patient
Comparison of number / percentages of SAE, AE, AESI, escape rate between the 2 groups (RDN-Treatment group vs. Sham group)
- Increase of serum creatinine / eGFR (calculated based on CKD-epi) between visit 3a (week 0) and visit 3b, and visit 3a and visit 4 (week +3) between the 2 groups (RDN-Treatment group vs. Sham group) and in each group separately

Following events will be presented at all-time points post-procedure comparing 2 groups

All-cause mortality
New onset ESRD (eGFR<15 mL/min/m ² or need for renal replacement therapy)
Significant embolic event resulting in end-organ damage
Renal artery perforation or dissection requiring an invasive intervention
Major vascular complications requiring surgical repair, interventional procedure, thrombin injection, or blood transfusion
Hospitalization for hypertensive or hypotensive crisis
Hospitalization for major cardiovascular or hemodynamic related events
New onset stroke
New onset myocardial infarction
Suspicion of new onset renal artery stenosis by renal duplex ultrasound

Following AESIs will be presented as a table at all time points post-procedure comparing 2 groups

- All-cause mortality
- Hypertensive emergency resulting in hospitalization
- Hypotensive emergency resulting in hospitalization
- Hospitalization for heart failure
- Stroke, transient ischemic attack, cerebrovascular accident
- Acute myocardial infarction (STEMI/non-STEMI)
- Any coronary revascularization
- End stage renal disease, the need for permanent renal replacement therapy (i.e. the need for dialysis); doubling of plasma creatinine, eGFR <15ml/min/1.73m²
- Any renal artery complication requiring intervention (e.g. dissection; perforation)
- Major access site complications requiring intervention
- Significant embolic events resulting in end organ damage
- Procedure-related pain lasting for > 2 days
- Acute renal injury, defined as:

- Increase in serum/plasma creatinine to ≥ 1.5 times pre-procedure visit (week -1) or decrease of eGFR (derived from creatinine, CKD-epi) by 25% known to have occurred during 7 days post procedure or
- Urine volume < 0.5 ml/kg/h for 6 hours

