1.2. Design of the Trial

RDN-CKD Study is a prospective, randomized (1:1, central randomization), double-blind (unblinded interventionalist and blinded study team at each center), sham controlled, multicenter feasibility study. All centers have participated at least in one of the sham-controlled trials in primary hypertension thereby having established an unblinded and a blinded team.

The RDN-CKD Study has been conducted at 5 clinical investigational sites, which are the University Hospitals in Erlangen, Homburg/Saar, Düsseldorf, Berlin and Nürnberg.

We aimed to include 80 patients with CKD stages 3a or 3b (according to the currently used estimation formulas [MDRD, CKD-EPI] and uncontrolled hypertension in the RDN-CKD study. This number of patients could not be achieved due to diverse reasons (pandemic, low recruitment). Therefore the recruitment got stopped by 31.12.2022.

If the patient fulfils inclusion criteria and in the absence of exclusion criteria at visit 1, the patient has been enrolled into the trial, and the study visits were scheduled. All subjects have their office BP measured, a limited medical history review, physical exam and current medication review and a safety laboratory evaluation. Furthermore, an ABP measurement was conducted. Visit 2 serves a FU in the run-in phase. All subjects were checked for medication adherence. A 24-h ambulatory BP measurement was conducted. Additionally, all subjects had their office BP measured, physical exam and current medication review and a safety laboratory evaluation. Once a subject has met all the screening criteria for the study the visit was scheduled for the renal angiogram and RDN/Sham procedure. Subjects of child bearing potential must have a documented negative pregnancy test dated within a maximum of 7 days prior to the procedure.

Randomization occurred following the diagnostic renal angiogram. Only randomized patients counted towards the enrollment ceiling. FU Visits took place 3 weeks, 6 weeks, 12 weeks, 19 weeks, 26 weeks, 39 weeks, 52 weeks post procedure. All baseline measurements were repeated 12 weeks, 26 weeks and 52 weeks post-procedure. Due to early recruitment stop of the study certain number of patients had only FU visits till 26 weeks post procedure.

Escape Criteria

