Enrolled subjects will be excluded if office BP exceeds $\geq 170/105$ mmHg confirmed by 7-day average of home blood pressure measurements \geq BP $> 160/100$ mmHg (excluding white coat effect) and confirmed by office BP $\geq 170/105$ mmHg at another study visit.

Unscheduled visit (UV)

In case subjects will be seen at additional times other than regular scheduled study visits, if deemed necessary by the Investigator, the following safety assessments will be performed: safety laboratory, urinalysis, vital signs, physical examination, AE assessment, checking concomitant medication.

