2.3. Analysis populations

For the analyses of the study, following populations are pre-specified:

1. The **Safety population (SAF population)** included all patients who provided informed consent
2. The **Intention-to-treat population (ITT population)** consisted of all randomised patients having a post-procedure measurement of at least one (primary) efficacy parameter.
3. The **modified ITT population (mITT)** include only participants from the ITT population without adherence violations.
4. The **Per Protocol population (PPP)** included all patients of the ITT population who did not show any major protocol violation (defined prior to unblinding of the data). These patients received at least two measurements of 24-h ambulatory BP (one pre-procedure (week -4 or week -1) and one 3 or 6 months post-procedure), performed in technically high quality.
5. The **Modified Per Protocol Population (mPPP)** include only patients of the PPP without adherence violations
6. The **Bavarian population** include only patients from 2 centres (Erlangen and Nürnberg)

Use of analysis sets

Demographic data and clinical characteristics of the patients will be displayed on all the pre-specified populations. Prior and concomitant medications as well as prior and concomitant medical conditions will be reported on all pre-specified populations.

The ITT population will be the basis for the primary analysis.

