2.4. Analyses

Statistical analyses will be based on the basis of international guidelines (CPMP/ICH/363/96:E9). Due to the early stop of the study, only an exploratory and descriptive analysis takes place. Statistical methods used to compare groups for primary and secondary outcomes:

Efficacy: Change of systolic 24-h ambulatory BP at 6 months post-procedure (primary efficacy endpoint) compared between the RDN and sham group will be analyzed in a linear mixed model including the covariates that were significantly different between the groups at baseline. All secondary (see 1.1.2) and observational endpoints (1.1.3 and 1.1.4) are analyzed also via a modelling approach adjusting for potential imbalances in baseline characteristics. The type I error for the analysis of the primary endpoint is set at 5% (two-sided), all analyses of secondary endpoints have an exploratory character avoiding multiplicity issues in this trial.

In addition, a win ratio analysis will be conducted, with the criteria 24h ambulatory systolic BP change > 5 mmHg, office systolic BP change > 10 mmHg, and decrease of medication as defined by following 3 parameters (number of antihypertensive drugs, drug burden index and antihypertensive load index).

Analysis will be performed for the following populations:

1. Primary analysis is based on *the intention-to-treat* (ITT) population consisting of all randomized study subjects that are all either RDN treated or sham treated.
2. A secondary analysis will be done with a *modified ITT* population (mITT) in which participants with adherence violations will be excluded (sensitivity analyses).
3. A secondary analysis will be done with the *per protocol population* (PPP) in which study subjects with predefined protocol deviations (defined prior to unblinding of the data) are excluded.
4. A secondary analysis will be done with the modified *per protocol population* (mPPP) in which study subjects of the PPP with adherence violation are excluded.
5. A secondary analysis will be done with the safety population (SAF) in which all study subjects signing informed consent are included.

6. A secondary analysis will be done with those patients that are investigated by the Erlanger and Nürnberger center (CRC staff), with a total of N=20 randomized patients (Bavarian cohort)

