2.9.3. Analysis of Demographic and other Baseline Characteristics

Demographic and patient characteristics will be summarized in tables and listings for the SAF, ITT, modified ITT, PPP, modified PPP, Bavarian population, separated by treatment groups and for the total population.

The demographic characteristics are: age and gender etc.

Summary of medical history and prior or concomitant medication will be presented.

The summary of medical history and current medical conditions including all previous and current medical conditions will be presented by preferred term and by body system of the system.

Baseline values of the efficacy measures will be presented in the efficacy section.

Baseline laboratory values will be presented.

Data from patients who were enrolled into the study, but not treated renal denervation or sham, will be presented in listings. No further analyses will be done with these patients' data.

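### Patients who meet the BP escape criteria after randomisation can leave the 6-month ABP comparison if ABP stops at escape, because the SAP does not fix their analysis set or the use of their ABP

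*SAP*

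**What the plan says.** **Escape rule.** Section 1.2 (Escape Criteria) states "Enrolled subjects will be excluded if office BP exceeds" 170/105 mmHg, confirmed by a 7-day home average above 160/100 mmHg and by a second office reading at another visit. It does not say whether exclusion is from the procedure, from follow-up or from analysis.

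**When it applies.** Section 1.1.5 plans a "Comparison of number / percentages of SAE, AE, AESI, escape rate between the 2 groups". Groups exist only after randomisation, so the rule is not confined to run-in.

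**Analysis sets.** Two definitions of ITT stand side by side:
- Section 2.3: the set "consisted of all randomised patients having a post-procedure measurement of at least one (primary) efficacy parameter".
- Section 2.4: the set "consisting of all randomized study subjects that are all either RDN treated or sham treated".

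Section 2.9.3 deals only with patients who were not treated: "Data from patients who were enrolled into the study, but not treated renal denervation or sham, will be presented in listings". The per-protocol set in 2.3 accepts an ABP from "one 3 or 6 months post-procedure".

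**Primary analysis.** Section 2.9.4.1 names an unpaired t-test at 6 months. Section 2.4 names a linear mixed model for the same endpoint and does not say which visits enter it. Section 2.7.1 leaves missing values blank and gives replacement rules for dates only.

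**Schedule.** Office BP is taken at weeks 3, 6, 12, 19 and 26. After the procedure, 24-h ABP is due at weeks 12, 26 and 52 (sections 1.3 and 2.7.3.1). It is not among the assessments listed for unscheduled visits.

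**The concern.** Escape is triggered by high BP, and BP is the outcome. If escape also ends ABP recording, the patients missing at 6 months are selected on something close to the endpoint. If RDN lowers BP, more of them come from the sham arm, so the two arms are trimmed unequally.

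Whether visits continue after escape is for the protocol. Which analysis set an escaper belongs to, and whether a week-12 ABP counts, is for the SAP. It gives two answers on the first and none on the second. The choice could then be made after unblinding.

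**Working it through.** **1. Tracing a treated escaper through the text, supposing ABP stops at escape**

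| Escape confirmed at | Post-procedure ABP on record | ITT by 2.3 | ITT by 2.4 | t-test in 2.9.4.1 |
|---|---|---|---|---|
| weeks 3 and 6 | none | out if the bracketed word (primary) is binding; in if office BP counts | in | lost |
| weeks 6 and 12 | week 12 due | in | in | lost |
| weeks 12 and 19 | week 12 | in | in | lost |
| weeks 19 and 26 | weeks 12 and 26 due | in | in | kept |

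The mixed model could keep the second and third rows through the week-12 ABP, but section 2.4 does not say that this value is used. If ABP continues after escape, nobody is lost through this route.

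**2. Size of the loss**

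The SAP gives no escape rate, SD or effect size, so there is no stated figure to reproduce and every input here is an assumption.

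Let an arm have escape fraction e, mean change m overall and mean change x among escapers. The mean among those kept is (m - e·x)/(1 - e), so dropping escapers shifts it by e(m - x)/(1 - e). Escapers have the worse change (x > m), so the shift is negative and looks favourable in each arm. The between-arm bias is the difference of the two shifts.

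The shifts were found by Monte Carlo with 700,000 patients per arm before screening, in 18 settings:
- baseline 24-h systolic BP 140, 145 or 150 mmHg (SD 10);
- office BP 8 or 12 mmHg above 24-h BP;
- correlation 0.5, 0.8 or 1.0 between BP changes at any two visits;
- SD of change 11, sham change -2, office noise SD 10, home BP 3 above 24-h BP with noise SD 6;
- systolic thresholds only, with patients who meet the rule before randomisation removed first.

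Results for a true difference of -6 mmHg:

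| Pair of visits counted | Loss, escapers dropped (mmHg) | Loss, mixed model on weeks 12 and 26 (mmHg) |
|---|---|---|
| 3 and 6 | 0.11 to 0.78 | 0.12 to 0.85 |
| 6 and 12 | 0.12 to 0.79 | 0.00 to 0.13 |
| 12 and 19 | 0.11 to 0.78 | 0.00 to 0.08 |
| all three | 0.22 to 1.09 | 0.14 to 0.85 |

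With one pair, escape is 1.9 to 11.4% in sham and 0.7 to 5.5% in RDN, and the median loss is about 0.35 mmHg. A repeat with separate code gave 0.11 to 0.80 for one pair and 0.23 to 1.16 for all three. By correlation, the one-pair maximum is 0.36 at 0.5 and 0.61 at 0.8; only 1.0 gives about 0.8.

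A second model used SD of change 12, office SD 16, mean follow-up office BP 145 to 160 mmHg and correlation 0.3 or 0.6. There -5 became -4.93 to -4.23, and -8 became -7.85 to -6.89.

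**3. No true effect**

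The between-arm difference stays within 0.03 mmHg of zero. Each arm's own mean change looks 0.19 to 1.73 mmHg too favourable with one pair. With the mixed model, where a week-12 ABP exists, this falls to 0.00 to 0.27.

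**4. Against the precision of the trial**

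The target of 80 was missed ("This number of patients could not be achieved due to diverse reasons", section 1.2), so there are fewer than 40 per arm. Section 2.4 counts 20 randomised in two centres, so there are at least about 10 per arm. With SE = 11 × √(2/n):
- n = 40: 11 × √0.05 = 2.46 mmHg
- n = 20: 11 × √0.10 = 3.48 mmHg
- n = 10: 11 × √0.20 = 4.92 mmHg

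The one-pair loss is therefore 0.11/4.92 = 0.02 to 0.79/2.46 = 0.32 SE. At 20 per arm, expected escapers are 20 × 0.019 to 20 × 0.114, or 0.4 to 2.3, in sham. In RDN they are 20 × 0.007 to 20 × 0.055, or 0.1 to 1.1.

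**The case against.** The best defence is that section 2.4 already keeps treated escapers: its ITT takes all randomised, treated subjects, and no set in 2.3 or 2.4 lists escape as a ground for exclusion. A reader might infer that the plan deletes escapers from ITT. The text does not support that. The risk comes from the stricter wording in 2.3 and from a t-test that needs a 6-month value, and set membership does not supply that value.

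It is also fair that section 1 is a protocol summary and that the loss arises only if ABP stops at escape. The SAP does not show that it stopped, or that any patient was lost. The conflict over ITT, the two primary methods and the lack of a rule for missing BP affect every dropout. Escape deserves separate mention because it is the one route triggered by the outcome itself.

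A reader might also infer a false-positive risk. The calculation shows none: the bias pulls toward no effect and vanishes when RDN does nothing. The expected count is about one or two patients, and section 2.4 calls the analysis exploratory and descriptive. All of this stands, and it is why the point is minor. Even so, a two-sided 5% test is set for this endpoint, so who enters it should be fixed.

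**Conclusion.** The point holds, as a minor one and on a condition. If 24-h ABP is not recorded after escape, the plan as written lets randomised patients leave the primary comparison because their BP was high. Under the assumed inputs the loss is roughly 0.1 to 0.8 mmHg of a true -6 mmHg, and up to 1.1 or 1.2 if every pair of visits before week 26 counts. It is conservative and well under one standard error. The effect on the between-arm test is therefore slight. The within-arm paired changes announced at the end of section 1.1.3 are more exposed, since they look too favourable in both arms whether or not RDN works. The direction follows from the escape rule. The size depends on escape rates and correlations that the document does not give.

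**What to change.** 1. **One ITT definition in 2.3 and 2.4:** all randomised patients, analysed as randomised, with no requirement for a post-procedure measurement. Limit the listings-only sentence in 2.9.3 to patients who were never randomised, so that it does not conflict.
2. **State in 1.2 and 2.3** that meeting the escape criteria after randomisation removes nobody from ITT or from the primary analysis.
3. **Make the mixed model of section 2.4 the primary analysis**, fitted to all recorded week-12 and week-26 24-h systolic ABP as repeated measures, including ABP after escape. Keep the t-test as supportive only.
4. **List escapers by arm**, with week of escape and whether a post-procedure ABP exists. Sections 1.1.5 and 2.9.2 already give the escape rate and reasons for discontinuation, so only these details are new.

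Carrying a week-12 value forward is not advised: in the simulation it overshot by up to 0.19 mmHg and recovered nothing for week-6 escapers.

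**Cost:** wording, one model specification and one listing, with no new data.

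**Downsides:**
- ABP after escape may reflect added drugs. If these lower escapers by 5 or 10 mmHg, the estimated effect shrinks by about that amount times the difference in escape rates. At the top this is (0.114 - 0.055) × 5 = 0.30 or × 10 = 0.59 mmHg; across the settings it is 0.06 to 0.29 or 0.13 to 0.59.
- Patients who escape by week 6 with no later ABP add no outcome data to the model and can only be listed.
- The SAP (01.09.2023) postdates the end of recruitment (31.12.2022), so it can settle the analysis but not how sites applied the rule.

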1.3. Trial Flow Sheet

Enrollment of subjects occurred at the clinical sites only after the appropriate local study approvals, “Approval to Enroll” documentation from the Sponsor and written informed consent from subjects have been obtained.

Visit #	V1	V2	V3	V4	V5	V6	V7	V8 ⁷	V9	V10
Week	-4	-1	0	3	6	12	19	26	39	52
Informed consent	X									
Inclusion/exclusion criteria	X									
Medical history	X									
RDN/Sham Procedure			X							
Physical exam	X	X	X	X	X	X	X	X	X	X
24-h ABP measurement ¹	X	X				X		X		X
Office (attended) BP ²	X	X	X	X	X	X	X	X	X	X
Safety and efficacy lab	X	X	X	X	X	X	X	X	X	X
AEs/ADEs	X	X	X	X	X	X	X	X	X	X
UACR ³ , eGFR, Cystatin C	X	X				X		X		X
Urinary toxicological analyses ⁴		X				X		X		X
Body fluid composition		X						X		X
MRA of Renal Arteries ⁵		X								
Duplex ultrasound ⁶		X								X
Medication review	X	X	X	X	X	X	X	X	X	X

Visit schedule (# all visits can be scheduled +/-5days)

- 24-h ambulatory BP measurements will be conducted by mobilograph (IEM, Aachen) allowing also the assessment of central systolic BP in addition to brachial BP readings.
- Office (attended) BP according to ESH guidelines with automated oscillometric device while nurse/physician is in the room (attended visits).
- UACR – albumin/creatinine ratio.
- To assess adherence to prescribed medication
- MRA has only to be performed if no images (previous MRI, previous CT, previous angiogram) of anatomy of renal artery supply is available
- If the last duplex sonography examination displays signs of renal artery stenosis or is not fully evaluable according to the investigator’s discretion, an angiogram needs to be performed to rule out or diagnose any renal artery abnormality which can be compared with the angiogram performed at baseline.
- Patients who will not have 12 months follow up visit until June 2023 but thereafter will have a shorter follow up period of 6 months only and unblinding will take place after all data of the 6 months FU visit have been entered and secured in the database (the rationale is that the primary objective is change in blood pressure after 6 months!

2. Outcome Measures and Target Parameters

2.1. Efficacy

Primary efficacy endpoint:

- Change in systolic 24-h ambulatory BP at 6 months post-RDN-procedure from pre-procedure (including 1. Pre-treatment value (**P**) = average of the pre-procedure visit (week -1) value and screening visit (week -4) value, 2. Baseline value (**B**) = pre-procedure visit

(week -1) value only) compared *between the 2 groups* (RDN-Treatment group vs. Sham group).

Secondary efficacy endpoints:

The secondary efficacy parameters of the study are:

- Change in systolic 24-h ambulatory BP at 3 and 12 months post-procedure from pre-procedure (including P and B) compared between the 2 groups (RDN-Treatment group vs. Sham group).
- Change in diastolic 24-h ambulatory BP at 3, 6 and 12 months post-procedure from pre-procedure (including P and B) compared between the 2 groups (RDN-Treatment group vs. Sham group).
- Change in office systolic and diastolic BP at 3, 6 and 12 months post-procedure from pre-procedure (including P and B) compared between the 2 groups (RDN-Treatment group vs. Sham group).
- Change in home systolic and diastolic BP at 3, 6 and 12 months post-procedure from pre-procedure (including B only) compared between the 2 groups (RDN-Treatment group vs. Sham group).
- Responder rate in BP (systolic office BP ≥ 10 mmHg, or 24-h systolic ambulatory BP ≥ 5 mmHg) at 3, 6, and 12 months post-procedure from pre-procedure (including P and B) compared between the 2 groups (RDN-Treatment group vs. Sham group).
- Change in serum creatinine, cystatin C at all time points from pre-procedure (pre-procedure visit (week -1) value and screening visit (week -4)) compared between the 2 groups (RDN-Treatment group vs. Sham group).
- Change in eGFR (calculated based on CKD-epi formula) derived from serum creatinine at all time points from pre-procedure (pre-procedure visit (week -1) value and screening visit (week -4)) compared between the 2 groups (RDN-Treatment group vs. Sham group). [1]
- Change in eGFR derived from cystatin C at all time points from pre-procedure (pre-procedure visit (week -1) value and screening visit (week -4)) compared between the 2 groups (RDN-Treatment group vs. Sham group). [2, 3]
- Change in eGFR derived from creatinine/Cystatin-C formula at all time points from pre-procedure (pre-procedure visit (week -1) value and screening visit (week -4)) compared between the 2 groups (RDN-Treatment group vs. Sham group) [3]
- Change of the slope of eGFR (derived from creatinine; CKD-epi formula) after half year and one year post-procedure from pre-procedure (pre-procedure visit (week -1) value and

screening visit (week -4) eGFR values) compared between the 2 groups (RDN-Treatment group vs. Sham group).

- Change of the slope of eGFR (derived from creatinine; CKD-epi formula) after half year and at 1 year post-procedure from pre-procedure (pre-procedure visit (week -1) value and screening visit (week -4) eGFR values) compared to the historical slope the year before
- Change in proteinuria (per g urinary creatinine), albuminuria (per g urinary creatinine), urine sodium (per g urinary creatinine), urine potassium (per urinary creatinine), urine creatinine concentration at 3, 6 and 12 months post-procedure from pre-procedure (pre-procedure visit (week -1) value and screening visit (week -4)) compared between the 2 groups (RDN-Treatment group vs. Sham group). Win ratio analysis will be conducted, with the criteria 24h ambulatory systolic BP change > 5 mmHg, and office systolic BP change > 10 mmHg at 3, 6 and 12 months from pre-procedure (including P and B) in both groups (RDN-Treatment group vs. Sham group). [4]
- Win ratio analysis will be conducted, with the criteria 24h ambulatory systolic BP change > 5 mmHg, office systolic BP change > 10 mmHg, and decrease of medication number at 3, 6 and 12 months from pre-procedure (including P and B) in both groups (RDN-Treatment group vs. Sham group). [4]
- Win ratio analysis will be conducted, with the criteria 24h ambulatory systolic BP change > 5 mmHg, office systolic BP change > 10 mmHg, and any decrease of drug burden index in both groups at 3, 6 and 12 months from pre-procedure (including P and B) in both groups (RDN-Treatment group vs. Sham group). [4]
- Win ratio analysis will be conducted, with the criteria 24h ambulatory systolic BP change > 5 mmHg, office systolic BP change > 10 mmHg, and any decrease of antihypertensive load index at 3, 6 and 12 months from pre-procedure (including P and B) in both groups (RDN-Treatment group vs. Sham group). [4]

Other Observational Efficacy Assessments:

- Change in average daytime/night-time ambulatory systolic BP at 3, 6 and 12 months post-procedure from pre-procedure (including P and B) compared between the 2 groups (RDN-Treatment group vs. Sham group).
- Change in average daytime/night-time ambulatory diastolic BP at 3, 6 and 12 months post-procedure from pre-procedure (including P and B) compared between the 2 groups (RDN-Treatment group vs. Sham group).
- Change in average daytime/night-time ambulatory heart rate at 3, 6 and 12 months post-procedure from pre-procedure (including P and B) compared between the 2 groups (RDN-Treatment group vs. Sham group).

- Change in average 24 hour ambulatory heart rate at 3, 6 and 12 months post-procedure from pre-procedure (including P and B) compared between the 2 groups (RDN-Treatment group vs. Sham group).
- Change in office heart rate at 3, 6 and 12 months post-procedure from pre-procedure (including P and B) compared between the 2 groups.
- Incidence of ambulatory systolic BP (daytime/24-h/night-time) reductions of ≥ 5 mmHg, ≥ 10 mmHg, and ≥ 15 mmHg at 3, 6 and 12 months post-procedure from pre-procedure (including P and B) compared between the 2 groups (RDN-Treatment group vs. Sham group).
- Percentage of subjects who are controlled in the absence of changes in hypertensive medication at 3, 6 and 12 months post-procedure compared between the 2 groups. (Four different criteria of “controlled” will be used: daytime ambulatory BP $< 135/85$ mmHg; night-time ambulatory BP $< 120/75$; 24-h ambulatory BP $< 130/80$ mmHg; office BP $< 140/90$ mmHg)
- Percentage of subjects who are controlled irrespective of any changes in hypertensive medication at 3, 6 and 12 months post-procedure compared between the 2 groups (Four different criteria of “controlled” will be used: daytime ambulatory BP $< 135/85$ mmHg; night-time ambulatory BP $< 120/70$; 24-h ambulatory BP $< 130/80$ mmHg; office BP $< 140/90$ mmHg).
- Change in office and 24 hour ambulatory pulse pressure at 3, 6 and 12 months post-procedure from pre-procedure (including P and B) compared between the 2 groups.
- Changes in percentages of dipper/non-dipper patterns at 3, 6 and 12 months post-procedure compared between the 2 groups (Criteria for non-dipping is less than 10% decrease of night time systolic ambulatory BP from daytime BP).
- Change in number of antihypertensive drugs at 3, 6 and 12 months post-procedure from pre-procedure (pre-procedure visit (week -1)) compared between the 2 groups.
- Change in drug burden index at 3, 6 and 12 months post-procedure compared from pre-procedure (pre-procedure visit (week -1)) between the 2 groups (RDN-Treatment group vs. Sham group).
- Change in antihypertensive load index at 3, 6 and 12 months post-procedure from pre-procedure (pre-procedure visit (week -1)) compared between the 2 groups (RDN-Treatment group vs. Sham group).
- Percentage of subjects requiring initiation of additional antihypertensive drug therapy between 3 and 6 months post-procedure compared between the 2 groups (RDN-Treatment group vs. Sham group).

- Change in following body fluid composition parameters measured by the Body Composition Monitor (BCM), Fresenius Medical Care at 3, 6 and 12 months post-procedure from pre-procedure (pre-procedure visit (week -1)) compared between the 2 groups (RDN-Treatment group vs. Sham group)
 - o Weight, height, BMI, Overhydration (OH), OH % of extra cellular water
- Change in following parameters at all ambulatory BP measurements (24 hours ambulatory values, ambulatory values- day time and ambulatory values- night time) derived from Mobilograph® examination at 3, 6 and 12 months post-procedure from (pre-procedure visit (week -1)) compared between the 2 groups (RDN-Treatment group vs. Sham group).
 - o Pulse pressure, zentral systolic pressure (zSys), zentral diastolic pressure (zDia), augmentation index at 75 beats per minute (AIx at 75 bpm), heart minute volume (HMFV), peripheral resistance, reflexion coefficient, pulse wave velocity (PWV)

